The primary outcome: the proportion of participants who either progressed as planned, successfully completed the program by obtaining a (conditional) certificate of professional competence, or transitioned to employment as care assistants.

Secondary outcomes include:

- a societal business case and a qualitative analysis to assess the impact of the program on participants and departments
- the influence of competencies on the need for additional guidance
- potential unconscious and conscious racial microaggression in the workplace

Factors considered as potential confounders are:

- sociodemographic characteristics: age, gender, time since arrival in the Netherlands, and family situation
- educational and professional background: level and type of nursing qualification, years of work experience, and previous additional training
- language and cognitive capacity: baseline Dutch and English proficiency, learning capacity as assessed by the study skills test, and motivation and initiative
- programme-related/contextual factors: hospital/department, differences in mentorship/guidance during integration, regional labor market demand, adaptations or optimizations implemented within the program over time

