3.3 Research questions

What is the proportion of participants who progressed as planned or successfully complete the program at 3, 6, and 10 years after start of the programme? What is the societal business case of the programme and what opportunities for improvement can be identified to optimize its sustainability through a qualitative analysis of the impact on both participants and hospital departments? To what extent do competencies across different domains provide insight into when a participant may require additional support? To what extent do conscious or unconscious racial microaggressions occur in the workplace and what opportunities exist to address and mitigate the unconscious form?

4. Study design

4.1 Mono- or multicenter study.	Monocenter study 	Multicenter study 
--	--	--

4.2 Retrospective study or prospective study		Retrospective study 	Prospective study 
4.3 Cross-sectional or follow-up study		Cross-sectional study 	Follow-up study 
4.4 Quantitative or qualitative study		Quantitative study 	Qualitative study 
4.5 Pilot or explorative study?	Not applicable 	Pilot study 	Explorative study 

Explain why it is a pilot or explorative study.

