6.1 Data collected

For primary outcomes:

- Background: nurse, nursing assistant, other
- Start date of medical vocational language program
- Start date as assistant nurse
- End date as assistant nurse
- Start date as care assistant
- Early dropout/ withdrawal
- In case of premature exit: 1 during (vocational) language training (months 3-6); 2 during early stages of the employment trajectory (months 7-12); 3 later in the employment trajectory (months 12-18/24)
- Date dropout/ withdrawal
- Date of decision on the application for a statement of professional competence and whether one may begin practicing under conditions
- CBGV decision on the application for a statement of professional competence: 1 decision granting a statement of professional competence allowing conditional registration in the BIG register ("Work in your profession in the Netherlands for three months under the supervision of a healthcare professional with the same profession who is fully registered in the BIG register, to become familiar with the Dutch healthcare system, related laws and regulations, and medical ethics.") Diploma is nearly equivalent. 2 additional internships: X months of internship in a hospital, VVT (nursing and care facilities), and/or GGZ (mental health care). 3 diploma not equivalent: Not allowed to practice as a nurse in the Netherlands.
- Conditional BIG registration date (above profession) with BIG number
- Date of possible meeting with the CIBG committee in case of a failing oral exam result, while results for the knowledge and practical tests are sufficient
- Start date of supervised practice
- End date of supervised practice
- Supervised practice: full-time, parttime
- In case of internships, what type of internships?
- Start date of internships

- End date of internships
- Internships: full-time, parttime
- Theoretical modules
- Knowledge test result: insufficient, sufficient, good
- Knowledge test score
- Profession-specific test result: insufficient, sufficient, good, excellent
- Oral examination result: insufficient, sufficient, good, excellent
- Date of issuance of the statement of professional competence, enabling the colleague to qualify for (unconditional) registration in the BIG register
- Date on which the participant is officially registered in the BIG register after submission and approval of CCPS and CGC, etc.

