- Exit position: premature exit, exit as healthcare assistant, exit as BIG-registered nurse (or achievement of a comparable qualification at the paramedical level with a similar background)
- At exit: healthcare assistant or nurse – type of contract and number of hours: 1 Temporary (eg 1 year); 2 Permanent
- Start date as fully qualified nurse (possibly including onboarding period)
- Program underway and on track? program successfully completed; program still in progress and proceeding as planned; dropped out during the medical language program phase; dropped out during the assistant nurse phase due to insufficient background to continue; decided to stop BIG trajectory during assistant nurse phase and continue/start working as a care assistant; Other

For secondary outcomes and other outcomes:

Data to be completed by newcomer

- Years of education completed
- Country of training
- Attempts to have diploma recognized in the Netherlands
- Level achieved according to the diploma evaluation: A level that corresponds in Dutch terms to: diploma from senior secondary vocational education (MBO), qualification level 4, in nursing and care; 2 years of a nominal 4-year bachelor's program in higher professional education (HBO) in nursing; degree of bachelor in higher professional education (HBO) in nursing; degree of master in higher professional education (HBO) in nursing; other level
- Place of work experience: hospital, nursing home or care home, home care, other
- Years of work experience
- Last country you worked in before arriving in the Netherlands?
- Experience in the following types of hospital departments (multiple answers possible)
- Nursing tasks for which you are qualified: measuring blood pressure, wound care, removing stitches/sutures, preparing medication, venous puncture, inserting IV (intravenous) line, inserting urinary catheter, inserting nasogastric tube, resuscitation / CPR (cardiopulmonary resuscitation)
- As a nurse in the hospital, you have day, evening, and night shifts. Each shift lasts 8 hours. What is your attitude towards evening and night shifts? No problem, I am used to working these shifts; It will take some getting used to, but I think I can manage this with my private life; It is difficult to reconcile with my private life
- Years living in the Netherlands at time of entry
- Socioeconomic status at the time of entry

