- Reason for rejection? different background than nursing; background as midwife/nurse where previous cases show insufficient experience in the nursing domain to participate in the newcomers program; has a nursing/caregiving background but does not have at least an MBO4 diploma equivalence; not sufficiently learnable according to language center / Study Skills Test; too little practical experience; practical experience too long ago; no status yet; residing outside regions participating in the newcomers program; language development not yet sufficient; may be considered later if appropriate language development is shown; too busy to participate in the program due to integration activities, searching for housing, etc.; other reason
- Living situation during the program? already own housing; medical vocational language program started from COA location, moved during the program to linked municipality; not residing at COA location or own housing, other
- Unlinked from previous municipality, linked to the municipality of Groningen? after obtaining status, linked to the municipality of Groningen within the program; unlinking from previously linked municipality, and linking to the municipality of Groningen within the program; already linked to a municipality near the hospital where the participant will start, within the newcomers program; not applicable
- reason for starting as a care assistant instead of assistant nurse (optionally indicate in which hospital as care assistant and where the participant may have worked as assistant nurse)
- Hospital name
- Type of department
- Extra guidance needed
- Type of additional support
- Cause of early dropout/ withdrawal
- Date of application received for a statement of professional competence for the nursing profession

 - Date of General Knowledge and Skills test - Date of profession-specific test 
Various durations are automatically calculated, including:
 
 - Working as an assistant nurse - From start as assistant nurse to date of profession-specific test - From date of profession-specific test to conditional BIG registration - Work under supervision - Internships - From start as assistant nurse to unconditional BIG registration - From start of medical vocational language program to date of early dropout - From start of medical vocational language program to start as assistant nurse 			

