Appendix 2:

Ontworpen fasttrack integration trajectory: The language centre of the University of Groningen developed a vocational language course as part of this project:

Vocational language course

General Course Outline – Customized Program: The specialized language course for nurses focuses on the essential language skills needed in nursing practice. It is based on the book 'De taal van de verpleging', designed for foreign healthcare professionals at A2 level, with word lists in English, Polish, Lithuanian, and Spanish. The course also incorporates contemporary texts, videos, websites, and other relevant materials. Practical Information: The course consists of 24 lessons, held twice a week, each lasting 2 hours, for a total of 48 contact hours. Additionally, at least 48 hours of self-study are required. The program runs for approximately 3 to 3.5 months.

Once participants reach the minimum Dutch language level (A2), they are required to successfully complete this 3.5 month course. Additionally, the UAF offers separate intercultural communication courses for both participants and their ward nurse mentors ('buddies'):

Intercultural communication training for newcomers and buddies For Newcomers

Goal: Communication is essential in healthcare. Whether engaging in a conversation with a client, discussing matters with family members, or handing over information to colleagues, effective communication plays a key role. In any conversation, it is not only the words spoken that matter—facial expressions and body language (non-verbal communication) are equally important. During the intervision meetings, we address questions and challenges from daily work practice, particularly those related to cultural differences, language, and communication. Additionally, we cover the following topics:

- Perspectives on health, illness, birth, and death across different cultures
- Various levels of cultural differences
- Indirect and direct communication styles
- Differences in time perception
- Understanding personal space
- Developing intercultural sensitivity

The training focuses on Dutch workplace culture and provides insights into communication, cultural awareness, and the skills needed to function effectively. It explores written and unwritten rules, direct and indirect feedback, time management, and workplace behavior and attitudes.

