- 1 – the knowledge test – includes various elements such as practicing sample questions, completing assignments, attending lessons, becoming familiar with clinical conditions, and gaining understanding of different healthcare sectors, including psychiatry, hospital care, elderly care, home care, and care for individuals with intellectual disabilities.
- 2 – nursing skills – includes, among others, dosage calculations and practice in the skills lab for procedures such as bladder catheterization, injections, feeding tubes, and peripheral IV insertion. As part of component
- 3 – the clinical reasoning interview – participants practice with clinical case studies.

The phases last approximately 4–6, 6–8, and 4–6 months, respectively. Participants are paired with one or two dedicated nurse buddies for onward support and to help set learning objectives. Additional support, such as extra language assistance or coaching by a medical content advisor, is available if needed.

In addition to medical guidance, a key aspect of the programme is the tailored support provided in areas such as municipal contact, registration in the Dutch healthcare system, and, where needed, engagement with other relevant organisations. A project leader with expertise in supporting healthcare newcomers was appointed.

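### The on-track status item has no level for participants still in progress but behind plan, and no rule defines 'as planned', which counts as success in the primary outcome

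*Protocol*

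**What the plan says.** Section 3.2 defines the primary outcome as "the proportion of participants who either progressed as planned, successfully completed the program by obtaining a (conditional) certificate of professional competence", with a move to care-assistant work as a third route to success. Section 3.3 asks for this proportion "at 3, 6, and 10 years after start of the programme".

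The last item listed for the primary outcome in Section 6.1 asks whether the programme is underway and on track. It has six answers:

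1. completed;
2. in progress and on plan;
3. dropped out in the language phase;
4. dropped out in the assistant-nurse phase for insufficient background;
5. left the registration route for care-assistant work;
6. a residual category.

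The second and third read "program still in progress and proceeding as planned; dropped out during the medical language program phase". The fifth and sixth read "decided to stop BIG trajectory during assistant nurse phase and continue/start working as a care assistant; Other".

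The same section collects milestone dates, beginning with "Start date of medical vocational language program". It also records test results, the competence decision and internship dates, and adds: "Various durations are automatically calculated, including" the time from course start to assistant-nurse start and several intervals after that. Appendix 2 gives planned lengths. For the language course it says "The program runs for approximately 3 to 3.5 months", and for the three hospital phases "The phases last approximately 4–6, 6–8, and 4–6 months, respectively".

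**The concern.** An active participant can be on plan or behind it. The endpoint treats the first as success, so the second has to be recordable as something else. The item asks about exactly this distinction but names only the favourable side.

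The protocol itself foresees events that slow people down: insufficient test results, a committee meeting after a failed oral examination, additional internships, and extra language help. Section 3.1 presents slow integration as the problem the programme is meant to solve. Delay is therefore central to what the endpoint should show.

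At stake is the main descriptive result. If delayed participants default to the on-plan answer, the proportion is biased in the programme's favour. If they go to 'Other', people still working towards registration are pooled with people who have left, and the reader cannot separate them.

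**Working it through.** The protocol states no figure that depends on this item, so there is none to reproduce. The check sets the answer list against the endpoint and the other data collected.

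**Answer list.** Of six answers, one is explicitly in progress (on plan only), none is in progress but delayed, and one is residual. The assistant-nurse drop-out answer covers insufficient background only. A drop-out in that phase for another reason has no named answer and also falls into 'Other'.

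**Rule.** The protocol gives no point at which a participant stops being on plan, does not connect the calculated durations to the status item, and does not say how 'Other' enters the primary proportion.

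**Can delay be derived?** Largely, from overall lengths in Appendix 2:
- hospital phases: 4 + 6 + 4 = 14 months to 6 + 8 + 6 = 20 months;
- with the language course: 3 + 14 = 17 months to 3.5 + 20 = 23.5 months.

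Course start and assistant-nurse start are both recorded, so time in each part can be computed up to the date of a look. Section 6.1 lists no start or end dates for hospital phases 1, 2 and 3, so a phase-by-phase comparison is not possible.

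**Does it matter at the planned looks?** Section 3.3 can be read in two ways.
- *Clock per participant.* Anyone still in progress at 3 years is at least 36 − 23.5 = 12.5 months beyond the summed lengths, yet the only named in-progress answer calls that person on plan.
- *Calendar clock from programme start.* With uniform enrolment and no drop-out (assumptions), the share still within the planned length is 17/36 to 23.5/36, or 47–65%, at 3 years, and 17/72 to 23.5/72, or 24–33%, at 6 years. At 10 years few would remain, because Section 6.3 projects enrolment only to March 2031 and the programme appears to date from about 2022 (assumption).

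**Illustrative size.** Shift in the primary proportion = (share in progress) × (fraction of those delayed), if all delayed participants are coded as on plan. Neither share is in the document.

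| In progress | Delayed among them | Shift (points) | of 159 | of 227 |
|---|---|---|---|---|
| 20% | 10% | 2 | 3 | 5 |
| 40% | 25% | 10 | 16 | 23 |
| 60% | 50% | 30 | 48 | 68 |

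Narrower assumptions of 30–50% in progress and 10–30% delayed give 0.30 × 0.10 = 3 points to 0.50 × 0.30 = 15 points. If delayed participants are coded 'Other' and counted as non-success, this inflation does not arise.

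**The case against.** The strongest reply is that little is lost. 'Other' can hold a delayed participant. Failed tests, internships and slow phases each leave a trace in the results, dates and durations. The status item is one of many listed for the primary outcome, and no sentence says the numerator is read from it alone. How the endpoint is built could sit in a separate analysis plan. The study is also descriptive, a pilot and exploratory.

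Much of this stands, and it rules out several stronger readings that a reader might infer:
- *The plan cannot detect delay, or does not measure it.* Not supported, given 'Other' and the recorded dates and results.
- *Participants can be checked against 6, 8 and 6 months phase by phase.* Not supported, because phase dates are not listed.
- *Anyone sent on additional internships is off plan.* Not stated. Section 6.1 treats internships as one possible outcome of the competence decision, and Appendix 2 gives lengths for the course and hospital phases only.
- *Hospitals will code differently.* Not supported. Section 9.2 has a single study coordinator completing essential outcome data, although Section 6.1 does not say who fills in this item.

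The reply does not remove the point about the answer list. That list is a data-collection choice fixed in this protocol, and an analysis plan can work around it only by deriving the status from other fields. Section 6.5, where the form asks for the analysis plan, refers to completion and registration and gives no on-plan rule. A descriptive aim makes the coding of the main proportion more important, because that proportion is the result.

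**Conclusion.** The concern holds in a limited form. The status item lacks a level for participants who are in progress but behind plan, and no stated rule separates on plan from behind plan, although being on plan counts as success. Delayed participants are therefore coded by judgement, either as successes or into a residual category shared with exits. The data to resolve this are mostly collected but not connected to the status.

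The bias is upward where delayed participants are coded as on plan. Its size cannot be taken from the document, and every percentage-point figure above is illustrative and rests on assumed shares. On a calendar clock it would matter most at the earlier looks. On a per-participant clock it concerns whoever is still active at 3 years or later. The change is worth making because the item bears on the primary outcome and the correction is cheap.

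**What to change.** - Add an answer for in progress but behind plan, and do not count it as success.
- At each look, derive 'as planned' by one written rule from recorded milestones: time from language-course start to assistant-nurse start, and total time since assistant-nurse start. Compare these with the overall lengths in Appendix 2 (about 3–3.5 months and 14–20 months), not phase by phase. For people who have not reached the next milestone, count up to the date of the look.
- State a tolerance. The lengths are approximate, and Section 6.1 itself places language-training exits in months 3–6.
- State whether time in required internships counts as on plan.
- State how the remaining 'Other' cases count in the numerator and denominator.
- Apply the rule identically at all hospitals and to those of the 49 already enrolled who give the additional consent.

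The cost is one extra answer level and one derived variable, mostly from dates already collected. The success proportion may come out less favourable.

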6.5 Statistical and/or qualitative analysis			
Please specify Statistical Analysis Plan (SAP): a. Description of study population: The study population consists of nursing newcomers who are already enrolled or will enrol in the fast-track integration trajectory at UMCG and participating partner hospitals. This includes both asylum seekers and migrants. Demographic and baseline characteristics include age,			

gender, language proficiency, participant status (asylum seeker or migrant), and socioeconomic and employment background. Participants who provide consent for research purposes will be included in the analysis.

b. Description of preparation of the data for analyses:

Collected data will be pseudonymized and direct identifiers removed. Data cleaning will involve checking for completeness, consistency, and plausibility. Variables will be coded according to pre-specified categories (e.g. employment history, language level). Missing data will be handled using appropriate methods such as multiple imputation or sensitivity analyses, depending on the extent and pattern of missingness. For qualitative data from surveys or interviews, responses will be anonymized and transcribed for coding and thematic analysis.

c. Specify all applicable statistical and/ or qualitative methods. This usually requires an extensive description of the planned analyses and covariates:

Primary outcome analysis: Descriptive statistics and inferential analyses (e.g. proportions, means, standard deviations) will be calculated for successful trajectory completion, BIG registration achievement. Associations with baseline characteristics will be explored using logistic regression or other appropriate multivariable models.

Secondary outcome analysis: Qualitative data from the Regioplan survey will be analyzed using thematic analysis to identify patterns, facilitators, and barriers in the trajectory. Quantitative secondary measures (e.g. language progress, employment outcomes) will be summarized using descriptive statistics and, where appropriate, tested with regression models to explore predictors of success.

Subgroup analyses will consider variables such as asylum seeker vs. migrant status, age groups, gender, and baseline language proficiency.

d. Clarify how this analysis plan, study setup, sample size and design will answer the study questions:

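### Durations are to be summarised descriptively with no rule for people still in progress, leavers or switchers, so early reports of time to BIG registration and of assistant-nurse time can come out too short

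*Protocol*

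**What the plan says.** Section 6.1 ends its data list, under the part for secondary and other outcomes, with the line "Various durations are automatically calculated, including". The items include time worked as assistant nurse, "From start as assistant nurse to unconditional BIG registration" and "From start of medical vocational language program to date of early dropout". No formula, analysis population or rule for unfinished intervals is attached.

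The same section collects the underlying fields. There is one "End date as assistant nurse", whatever the reason for ending. There is also "Date dropout/ withdrawal", a start date as care assistant, an on-track status that identifies people still in progress, and "Exit position: premature exit, exit as healthcare assistant, exit as BIG-registered nurse".

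In section 6.5c the primary analysis reads "Descriptive statistics and inferential analyses (e.g. proportions, means, standard deviations) will be calculated". The object of that sentence is completion and BIG registration, not durations. Quantitative secondary measures are to be summarised descriptively and, where suitable, put into regression models. Section 6.5b offers multiple imputation or sensitivity analyses for missing data in general. No censoring, time-to-event or competing-event method is named.

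Section 3.3 sets the looks "at 3, 6, and 10 years after start of the programme" without saying whether that start is the programme's or the participant's. Section 6.3 projects enrolment until March 2031.

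**The concern.** Two separate mechanisms pull the reported times downward.

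- **Time to registration.** The interval has no value until registration happens. With staggered entry and a calendar look, a slow participant is less likely than a fast one to have finished by the look. A mean over those with a value therefore over-represents quick finishers. The effect fades as follow-up matures, so reported time would seem to lengthen from look to look with no real change.
- **Time as assistant nurse.** For a leaver or switcher this interval ends on the day they stop. Pooled with completers, an early exit counts as a short phase, so more attrition makes the phase look quicker.

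The introduction describes delay as part of the problem the programme addresses and says phase durations were collected prospectively. Readers are therefore likely to look at these figures.

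**Working it through.** **Plan figures that can be reproduced.** The protocol states no duration result. Its enrolment figures do reproduce: 49 + 98 + 80 = 227, and 0.70 × 227 = 158.9, so 159 (section 6.3). The three assistant-nurse phases in Appendix 2 add to 4 + 6 + 4 = 14 up to 6 + 8 + 6 = 20 months, mid-range 17. The language course takes 3.5 months (Appendix 2) and supervised practice under conditional registration three months (section 6.1).

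**Will people be in progress at a look?** Someone entering in March 2031 needs about 3.5 + 14 + 3 = 20.5 to 3.5 + 20 + 3 = 26.5 months, so would register around November 2032 to May 2033. If the programme is dated from the March 2022 survey (assumption), the 10-year look falls in March 2032, before that. On the calendar reading, some participants are unfinished at every look.

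**Time to registration, calendar looks.** Assumptions, because the protocol gives no distribution: entry uniform over E months; T, from assistant-nurse start to registration, normal with mean 20 (SD 5) or mean 24 (SD 6); no exits. A participant is observed at look L if entry + 3.5 + T ≤ L. A person with time t is then observed with probability w(t) = (L − 3.5 − t)/E, limited to 0 to 1, and the mean among the observed is ∫ t f(t) w(t) dt / ∫ f(t) w(t) dt. At L = 36, someone needing 24 months must have entered in the first 36 − 3.5 − 24 = 8.5 months. Someone needing 15 months could have entered in the first 17.5.

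| Look | E (months) | True mean 20: observed mean (share registered) | True mean 24: observed mean (share registered) |
|---|---|---|---|
| 3 years | 36 | 18.0 (35%) | 20.2 (24%) |
| 6 years | 72 | 19.5 (67%) | 23.2 (62%) |
| 10 years | 108 | 19.7 (89%) | 23.6 (86%) |

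The shortfall is 2.0 to 3.8 months at 3 years, 0.5 to 0.8 at 6 years and 0.3 to 0.4 at 10 years.

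A second set of assumptions shows how far this depends on spread. It used 49 entries in months 0 to 36, 178 in months 36 to 108, phases drawn from the Appendix 2 ranges, and a delay to registration of exactly 3, 3 to 12, or 3 to 24 months. The shortfall was 0.1 to 6.4 months at 3 years, 0 to 1.4 at 6 years and at most about half a month at 10 years. It is near zero when times vary little.

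**Time to registration, looks from each participant's own start.** Observed now means T ≤ L − 3.5, a truncated normal with mean μ − σφ(b)/Φ(b), where b = (L − 3.5 − μ)/σ. At 3 years b = (32.5 − 20)/5 = 2.50 or (32.5 − 24)/6 = 1.42, giving means of 19.9 and 23.0. The shortfall is 0.1 and 1.0 months, and zero to one decimal at 6 years.

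**Time as assistant nurse.** With completers at 17 months, leavers at x months and a share d of leavers, the pooled mean is (1 − d) × 17 + d × x.

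- x = 5: 15.8, 14.6 and 13.4 months at d = 10, 20 and 30%, a loss of 1.2 months per 10 points.
- Exits spread over 3 to 14 months of assistant-nurse work (simulated, 10-year look): 16.1, 15.2 and 14.3 months, a loss of 0.9 per 10 points.

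Here x counts from assistant-nurse start. Section 6.1 codes exits in months 3 to 6 as language-training exits, which do not enter this interval. If its months count from course start (assumption), exits in months 7 to 12 fall 3.5 to 8.5 months into assistant-nurse work.

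**The case against.** The strongest reply is that section 6.1 is a list of database fields, not an estimator. No formula is printed and nothing says leavers will be pooled with completers. The means and standard deviations in 6.5c attach to completion and BIG registration. Dropout date, exit position and on-track status are all collected, and time to dropout is a separate field. Censoring rules for descriptive durations may also sit in a fuller analysis plan that is not shown.

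Most of this stands, and it limits the point. It does not remove it: the protocol places the durations among the secondary and other measures and names a method for quantitative secondary measures. That method, applied to an interval that exists only after its event, gives the distortion described. General provision for missing data does not cover it, since a pending registration is censored and a leaver may never register.

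Three stronger readings are tempting and unsupported.

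- A reader might infer that only fast finishers will ever be counted. By 10 years most finishers are included and the shortfall is small.
- A reader might infer that the plan will overstate a claim of speed. No duration is a primary outcome, a listed secondary outcome or a research question, and no comparison route is named.
- A reader might infer that the error carries into the business case. The data that sections 8.4 and 8.5 list for the external partners contain no durations, and the 4 to 6 months of salary cost in 6.3 are not tied to these fields.

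**Conclusion.** The point holds in limited form, at minor to moderate severity. The direction of both biases is clear: reported times come out short.

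For time to registration the size is about 2 to 4 months at a 3-year calendar look under assumed true means of 20 to 24 months. It is small by 10 years, and largely absent if looks run from each participant's own start. The protocol does not settle which applies. For assistant-nurse time it is roughly 1 month per 10 percentage points of leavers, at any look, but only if exits are pooled with completers. The leaver share, exit times and spread of registration times are assumptions. The primary proportion is not affected by this point.

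**What to change.** In section 6.5c:

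- Report time from language-course start, and from assistant-nurse start, to unconditional BIG registration as a cumulative incidence over everyone who started. Treat premature exit and switch to care assistant as competing events, and censor only those still in progress at the look date. Exits should not be censored, because that would treat leavers as still able to register.
- Report time as assistant nurse separately by exit position, not pooled.
- State whether 3, 6 and 10 years count from programme start or from each participant's start.

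The cost is wording and a standard competing-risk analysis; the dates and exit states needed are already collected. Reported times will be somewhat longer, and the median time to registration may not be reached at the first look.
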